5.5.4.3.1 Analysis of Other Secondary Efficacy Endpoints for Phase B and Phase A

Descriptive statistics will be provided by visit for change from baseline to End of Phase B in MADRS Total Score, CGI-S, SDS scores; analysis will be provided by visit in Phase B. These analyses will be based on OC data at each Phase B visit and the LOCF data at the last visit of Phase B, using Phase B Efficacy Sample. Baseline for Phase B will be the same as the baseline for Phase A for all above efficacy endpoint. Time to discontinuation due to all causes will also be examined in Phase B starting from the first dose of study medication taken in Phase B to discontinuation or completion.

Efficacy scales assessed during Phase A will be provided in listings for the Phase A Safety Sample.

5.5.4.3.2 Technical Computational Details for Other Secondary Efficacy Analysis

- 1) In general, data for MADRS, CGI-S, and SDS assessment after the relapsed dates for the relapsed randomized subjects will not be included in the Phase C efficacy summary tables.
- 2) Time to discontinuations due to all causes rather than the sponsor discontinued trial will be measured from the date of randomization to date of early termination for withdrawn subjects in Phase C, i.e., time to discontinuation = discontinuation date - randomization date +1. Subjects discontinuing the trial due to the sponsor discontinued trial in Phase C will yield censoring observations for time to discontinuation and be considered censoring at discontinuation, i.e., time to censor= discontinuation date - randomization date +1. Subjects completing the entire treatment duration of Phase C will yield censoring observations for time to discontinuation and be considered censoring at completion, i.e., time to censor= completion date - randomization date +1. If time to discontinuation/completion is great than 196 days, the subject will be considered as censoring at Day 196, no matter if he/she discontinued or completed Phase C.

Time to discontinuation due to all causes rather than the sponsor discontinued trial in Phase B will be calculated for Phase B efficacy sample using the similar method. Time to discontinuations due to all causes rather than the sponsor discontinued trial in Phase B will be measured from the 1st dosing date of Phase B to date of early termination for withdrawn subjects in Phase B, i.e., time to discontinuation in Phase B = discontinuation date - 1st IMP dosing date of Phase B +1. Subjects discontinuing the trial due to the sponsor discontinued trial in Phase B will yield censoring observations for time to discontinuation and be considered censoring at discontinuation, i.e., time to censor= discontinuation date - 1st IMP dosing date of Phase B +1. Subjects continuing into Phase C will yield censoring observations at randomization date, i.e., time to censor in Phase B = randomization date - 1st IMP dosing date of Phase B +1. If time to discontinuation/censor is great than 98 days, this subject will be considered as censoring at day 98 no matter if she/he is randomized into Phase C.

- 3) Computing of Scale Scores
 - a) The CGI-S and CGI-I of 0 will be set to missing because value means ‘not assessed’.

The MADRS consists of 10 items, all rated on a scale of 0 to 6 with 0 being the “best” rating and 6 being the “worst” rating. The MADRS Total Score is the sum of ratings for all 10 items. The MADRS Total Score will be un-evaluatable if more than 2 items are missing. If 8 or 9 of the 10 items are recorded, the MADRS Total Score will be the mean of the recorded items multiplied by 10 rounded to the first decimal place.

The CGI consists of two scales: CGI Severity (CGI-S), and CGI Improvement (CGI-I). CGI-S items are: 0 = not assessed; 1 = normal, not at all ill; 2 = borderline mentally ill; 3 = mildly ill; 4 = moderately ill; 5 = markedly ill; 6 = severely ill; 7 = among the most extremely ill patients. The score 0 (= not assessed) will be set to missing. The CGI-S is therefore a 7-point scale from 1 through 7.

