Urine drug screen ^g								X				
Urine pregnancy test (WOCBP only) ^h				X				X				X
SAS				X								X
AIMS				X								X
BARS				X								X
C-SSRS	X	X	X	X	X	X	X	X	X	X	X	X
Adverse events	X	X	X	X	X	X	X	X	X	X	X	X
Concomitant medications	X	X	X	X	X	X	X	X	X	X	X	X
Other												
Randomization												X
IMP dispensing	X	X	X	X	X	X	X	X	X	X	X	X

Protocol 331-201-00079

Assessment	Week 9 (\pm 2 days)	Week 10 (\pm 2 days)	Week 11 (\pm 2 days)	Week 12 (\pm 2 days)	Week 13 (\pm 2 days)	Week 14 (\pm 2 days)	Week 15 (\pm 2 days)	Week 16 (\pm 2 days)	Week 17 (\pm 2 days)	Week 18 (\pm 2 days)	Week 19 (\pm 2 days)	Week 20/ Random- ization/ ET ^{a,b} (\pm 2 days)
IMP accountability	X	X	X	X	X	X	X	X	X	X	X	X
Pharmacokinetic samples								X				X
Pharmacogenomic sample												X ^c

^aFor subjects who meet stability criteria, the Week 20 visit, Randomization, will be the baseline visit for all subsequent Phase C visits; for subjects who do not meet the stability criteria, the Week 20 visit will be the ET visit. Stability criteria are defined in the blinded addendum to this protocol.

^bIf a subject discontinues prematurely, procedures noted for Week 20 must be completed at the ET visit.

^cIncludes waist circumference.

^dVital signs include body weight, body temperature, SBP, DBP, and heart rate. Blood pressure and heart rate will be measured in the following order: supine, sitting, and standing after the subject has been in each position for at least 3 minutes. Vital signs scheduled for the same visit as blood samples are to be completed before blood is drawn.

^eStandard 12-lead ECGs will be performed after the subject has been supine and at rest for \geq 5 minutes prior to the ECG. ECG results will be evaluated at the investigational site to monitor safety. A central ECG service will be utilized to review all ECGs in order to standardize interpretations for the safety analysis. The ECG is to be completed before any blood sample is collected.

^fBlood samples for clinical laboratory tests must be drawn after a minimum 8-hour fast at the Week 20/Randomization visit and should be drawn after a minimum 8-hour fast at all other visits. If fasting blood samples are not feasible at visits other than the Week 20/Randomization visit, nonfasting blood samples may be collected. Vital sign and ECG assessments should be completed before any blood samples are collected.

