3.8.3.3 Documenting Reasons for Treatment Discontinuation

A subject may discontinue IMP for a number of reasons including those listed below:

- Reasons related to AE:
 - Subject decides to discontinue because of annoyance or discomfort due to a non-serious AE which is not otherwise determined to be an undue hazard
 - Continuing IMP places the subject at undue risk as determined by the investigator (eg, a safety concern that is possibly, probably, or likely related to IMP)
 - SAEs
 - Other potentially IMP-related safety concerns or AEs
- Death
- Reasons unrelated to medical condition (provide detail and review AE history with subject)
- Withdrawal of informed consent (complete written withdrawal of consent form)
- Lost to follow-up

Protocol 331-201-00079

- Pregnancy (see [Section 5.5](#))
- Termination of all or part of the trial by the sponsor

In addition, subjects meeting the following criteria must be withdrawn from the trial:

- Occurrence of any AE, intercurrent illness or abnormality in a laboratory assessment which, in the opinion of the investigator, warrants the subject's permanent withdrawal from the trial
- Treatment with a prohibited concomitant medication other than the use of appropriate medications for the treatment of AEs under direction of the investigator;
- Subject noncompliance, defined as refusal or inability to adhere to the trial schedule or procedures ([Section 3.12](#))
- At the request of the subject, investigator, OPDC or designee, or regulatory authority;
- Subject becomes pregnant
- Subject cannot tolerate the minimum dose of brexpiprazole (ie, 2 mg/day or matching placebo)
- Subject does not fulfill the response criteria by Week 8 of Phase A.
- Subject does not fulfill stability criteria by Week 12 of Phase B. In addition, subjects who have more than 3 excursions (ie, do not meet stability criteria at a scheduled visit) during Phase B and subjects with 3 consecutive excursions or an excursion on the last visit of the Phase B are to be withdrawn. A missed visit during Phase B will be considered an excursion.
- Subjects that do not maintain a stable dose of IMP or ADT for the last 4 weeks of Phase B
- Subject meets criteria for relapse in Phase C
- Subject is lost to follow-up

If the subject discontinues IMP due to an AE, the investigator, or other trial personnel, will make every effort to follow the event until it has resolved or stabilized. Follow up procedures in [Section 3.8.3.2](#) must be followed.

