5.1 Data/Data Sets Specifications

5.1.1 Data Sets Analyzed

The following analysis samples are defined for this trial:

- Enrolled Sample: All subjects who sign the informed consents form for the trial and enter Phase A or Phase B.
- Phase A Safety Sample: All subjects who receive at least one dose of brexpiprazole in Phase A.
- Phase B Safety Sample: All subjects who receive at least one dose of brexpiprazole in Phase B.
- Phase B Efficacy Sample: All subjects who enter Phase B (i.e., receive at least one dose of brexpiprazole in Phase B) and have at least one post-baseline efficacy evaluation in Phase B.
- Phase C Safety Sample: All subjects who are randomized to double-blind treatment and receive at least one dose of double-blind trial medication in Phase C.
- Phase C Efficacy Sample: Based on the Intent-to-Treat (ITT) principle, the full analysis set of this trial will be composed of all subjects randomized to the double-blind treatment who take at least one dose of IMP in Phase C.

For the primary analysis of time to event, all subjects belonging to the Phase C Efficacy Sample will be included in the analysis. Subjects who withdraw early from the trial or who are still in the trial at the end of Week 46 will be considered as censoring observations.

The observed case (OC) dataset will consist of the actual observations recorded at each visit and will be used to present summaries per trial week.

The last observation carried forward (LOCF) data set for Phase C will include data recorded at a given Phase C visit or, if no observation is recorded at that visit, data carried forward from the previous Phase C visit. Week 20 data (baseline of Phase C) will not be carried forward to impute missing values for the LOCF data set.

LOCF and OC data sets for Phases A and B will be derived in a manner similar to the process described for Phase C. Baseline of Phase A will not be carried forward to impute missing values for the LOCF in Phase B.

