5.5.4.3 Analysis of Other Secondary Efficacy Endpoints for Phase C

Baseline for Phase C is defined as the last visit of Phase B prior to the first dose of double-blind trial medication in Phase C. Analysis of the change from baseline for other secondary efficacy endpoints will be based on subjects in the Phase C Efficacy Sample. Analysis of the CGI-S score endpoint will be based on subjects in the Phase C Efficacy Sample who have post-baseline CGI-S observations. The analysis will be based on all subjects who have been randomized and taken one dose of IMP in Phase C.

The proportion of subjects meeting relapse criteria as defined in Primary Efficacy Endpoint Section 5.5.1.1 will be analyzed by treatment group, visit (OC) and the subject's last visit (LOCF) in Phase C using the Chi-square test.

Subjects maintaining remission is defined as MADRS total score ≤ 10 . Analysis will be done at each visit (OC) and the final visit (LOCF) using Chis-square test.

The MADRS, CGI-S score and individual SDS score at endpoint will be analyzed at the last visit (LOCF) using an ANCOVA model. As an exploratory analysis, change from baseline variables including MADRS, CGI-S, and SDS will be analyzed by a Mixed Model Repeated Measures (MMRM) approach using observed data, with terms of treatment, trial center, visit, treatment-by-visit interaction, baseline and baseline-by-visit interaction. To avoid too many parameters in the statistical model, variance-covariance matrix with heterogeneous compound symmetry structure is assumed in the MMRM analysis. In addition, the count and frequency of SDS with work/school item not applicable at baseline will be summarized.

The CGI-I score at endpoint will be analyzed at the last visit of LOCF data using the Cochran-Mantel-Haenszel method based on raw mean score statistics.

Kaplan-Meier curves will be plotted for time to discontinuation due to all causes and the log-rank test will be used to test the differences in the survival curves.

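### Censoring Phase B completers at their randomisation date can push the end of the Phase B time-to-discontinuation curve upward; a common Day 98 censoring day avoids this (minor, descriptive analysis only)

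*SAP*

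**What the plan says.** SAP 5.5.4.3.2 item 2 defines the Phase B measure by analogy with the Phase C one: "Time to discontinuation due to all causes rather than the sponsor discontinued trial in Phase B will be calculated for Phase B efficacy sample". Time runs from the first Phase B dose.

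- **Events** are dated at the "date of early termination for withdrawn subjects in Phase B". Sponsor termination is censored instead.
- **Completers:** "Subjects continuing into Phase C will yield censoring observations at randomization date".
- **Cap:** "If time to discontinuation/censor is great than 98 days, this subject will be considered as censoring at day 98".

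SAP 5.5.4.3.1 says that this measure will be examined in Phase B but names no estimator. The estimator appears in the Phase C section, SAP 5.5.4.3: "Kaplan-Meier curves will be plotted for time to discontinuation due to all causes".

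Protocol Table 3.7-2 gives the Week 20/Randomization/ET visit a window of ±2 days. Its footnote a adds that "for subjects who do not meet the stability criteria, the Week 20 visit will be the ET visit". Protocol 3.8.3.3 makes some Week 20 failures inevitable by rule: "subjects with 3 consecutive excursions or an excursion on the last visit of the Phase B are to be withdrawn".

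The Phase B Efficacy Sample (SAP 5.1.1) requires that subjects "have at least one post-baseline efficacy evaluation in Phase B".

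**The concern.** Censoring is meant for subjects whose event could still occur unseen. A randomised subject can no longer discontinue from Phase B, so the outcome is known. The SAP rule nevertheless removes these subjects from the risk set one by one over the few days in which Week 20 failures are being counted. Failures with slightly later dates are then divided by a shrinking denominator.

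The height of the curve at the end of the phase would therefore depend partly on the order of Week 20 dates, and could disagree with the disposition table in the same report. There is also a smaller mismatch: the clock starts at the first Phase B dose, but the sample requires a later efficacy rating, so subjects who leave with no Phase B rating are dropped from a measure of all-cause discontinuation.

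**Working it through.** **Inputs from the documents.** 700 enter Phase B and 450 are randomised (SAP 3.6 and Section 4; Protocol 7.1). Progression is stated as 68%. The Week 20 window is ±2 days and the cap is Day 98. Twelve weeks from Day 1 puts the target at 12 × 7 + 1 = Day 85, so the window is Days 83-87.

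**The plan's own figures.** 450/700 = 64.3%, not 68%; 700 × 0.68 = 476; 450/0.68 = 662. The two statements disagree, so both references are carried: 250/700 = 35.7% not randomised, and 224/700 = 32.0%.

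**Assumptions, not in the documents.** A share *s* of discontinuations falls at Week 20 and the rest before Day 83. Week 20 dates are spread evenly over five days, for failures and completers alike. Each failure is dated on the visit day. Events precede censorings at ties.

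**Formula.** With *d* failures and *c* randomisations per Week 20 day, let r = d/(d + c). The risk sets on the five days are 5, 4, 3, 2 and 1 times (d + c), so

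S(98) = [5(d + c)/700] × (1 − r/5)(1 − r/4)(1 − r/3)(1 − r/2)(1 − r).

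For 700/450, c = 90 and d = 50s. Example, s = 50%: d = 25, d + c = 115, and the risk set on Day 83 is 575. Then S = (575/700) × (550/575)(435/460)(320/345)(205/230)(90/115) = 0.821 × 0.585 = 0.481, so the estimate is 51.9%.

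| Share at Week 20 | d | Still in on Day 83 | Product of the five factors | Kaplan-Meier at Day 98, 700/450 (crude 35.7%) | Same, 700/476 (crude 32.0%) |
|---|---|---|---|---|---|
| 10% | 5 | 475/700 = 0.679 | 0.885 | 40.0% | 35.8% |
| 25% | 12.5 | 512.5/700 = 0.732 | 0.748 | 45.2% | 40.7% |
| 50% | 25 | 575/700 = 0.821 | 0.585 | 51.9% | 47.2% |
| 75% | 37.5 | 637.5/700 = 0.911 | 0.474 | 56.9% | 52.2% |

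The last column uses c = 476/5 = 95.2 and d = 44.8s.

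**Other date patterns, 700/450.**
- *All Week 20 dates on one study day.* With s = 50%, (575/700) × (450/575) = 450/700. The estimate is 35.7%, with no bias.
- *70% of visits on the target day, same-day dating.* Simulated means are about 41% to 64% for shares of 10% to 80%.
- *Failures dated after their visit.* If the last subject at risk is a failure dated by Day 98, the final factor is 1 − 1/1 = 0 and the estimate is exactly 100%. With lags of 1 to 7 days, simulated means are 99.6-100%. With lags of 10-13 days and spread visits they are about 88-90%, because some events are cut at Day 98.

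**Check of the fix.** If randomised subjects stay at risk to Day 98, nobody leaves the risk set between failures. The product telescopes to 450/700, giving 35.7% (or 32.0%) in every pattern with failures dated by Day 98.

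**Sample restriction.** If 2% or 5% of the 700 (assumed) left with no Phase B rating, the crude rate would become (250 − 14)/(700 − 14) = 34.4% or (250 − 35)/(700 − 35) = 32.3%.

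**The case against.** The strongest reply is that little depends on this curve. SAP 5.2 already tabulates the completion rate and reasons for discontinuation by phase in the enrolled sample, so retention is reported correctly elsewhere. The Phase B measure is single-arm and descriptive, with no test and no alpha. That stands, and it sets the severity.

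A reader might infer that the curve will read 40-57%, or nearly 100%, where the truth is 36%. The documents do not support that. They give neither the share of failures at Week 20 nor the spread of dates. Many failures may be withdrawn earlier, after more than three excursions or three consecutive ones. Read literally, the event is dated at the Week 20 visit itself, so the near-100% case needs a recording delay that the documents do not describe. Nor is 36% the only reference, since the stated 68% gives 32%.

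A reader might also take the Day 98 cap as proof that an end-of-curve estimate is intended. It may simply parallel the Phase C cap: 98 = 84 + 14 and 196 = 182 + 14. Kaplan-Meier for Phase B is likely but only implied.

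On the sample, it would be too strong to say that all the earliest leavers are lost. Protocol Table 3.7-2 footnote b requires Week 20 procedures, which include MADRS and CGI-S, at early termination. Only subjects with no Phase B rating at all drop out.

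What remains is that the rule treats a known outcome as unknown at the very visit where failures are counted.

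**Conclusion.** The concern holds as a conditional, minor point. If Phase B time to discontinuation is summarised by Kaplan-Meier under the written rule, the curve from about Day 83 can be biased upward. With same-day dating spread evenly over the window and 10-75% of discontinuations at Week 20, the excess is about 4 to 21 percentage points against 35.7% (40.0 − 35.7 to 56.9 − 35.7), or about 4 to 20 points against 32.0%. It is zero if the dates coincide, and the estimate could approach 100% if some failures are dated after the last randomised subject. Those shares and date patterns are assumptions.

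The curve before Day 83, the SAP 5.2 completion rate, and the primary and key secondary results are not affected. The efficacy-sample restriction works in the opposite direction; its effect is probably small, and the documents do not give its size.

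**What to change.** In SAP 5.5.4.3.2 item 2:

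1. Censor subjects who continue into Phase C at the common Day 98, not at the randomisation date. Alternatively, report cumulative incidence of discontinuation with randomisation as a competing outcome.
2. Name the Phase B estimator explicitly.
3. Use the Phase B Safety Sample, already defined in SAP 5.1.1, in place of the Phase B Efficacy Sample.

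The end-of-phase estimate should then agree with the disposition table, apart from two exceptions worth stating: subjects censored because the sponsor stops the trial (possible after a positive interim analysis, Protocol 3.8.1), and discontinuations dated after Day 98.

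The cost is a few wording changes and one derivation rule. No new data are needed.

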5.5.5 Sub-group Efficacy Analysis

Sub-group analysis of the primary endpoint in Phase C will be provided by region (US and non-US), gender (male and female), race (Caucasian and non-Caucasian), and age (<45 years old and ≥45 years old at Phase C baseline). Subgroup analyses will be performed for the FAS. To explore the beneficial effects of brexpiprazole vs placebo in the subgroups, the estimated hazard ratio, two-sided nominal 95% confidence interval, and within subgroup p-value from the log-rank test will be provided for each of the subgroups based on the Cox's proportional hazards model in which treatment is included as the fixed-effect factor. It should be aware that positive findings from these subgroup analyses have to be interpreted with caution since there is a non-negligible chance of false positives.

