7.4.4 Interim Analysis

Two interim analyses are planned for assessment of efficacy. These analyses are planned to be performed following a group sequential approach at approximately 50% and 75% of events accrual time points and will include all randomized subjects. The second interim analysis (at 75% of events) will be performed only if the first interim analysis is not positive. Subjects who withdraw early from the trial or who are still in the trial at the end of Week 46 will be considered as providing censored observations. The O'Brian-Fleming boundaries will be used for the interim analysis so that the first interim analysis will be conducted when 52 relapse events are available and the second interim analysis, if needed, will be conducted when 78 relapse events are available (Table 7.4.4-1).²⁸ The 2-sided alpha levels for these two interim analyses are 0.003051 and 0.018325 respectively, and the alpha left for the final analysis will be 0.044005. Additionally, a 95% confidence interval for the hazard ratio (brexpiprazole + ADT vs placebo + ADT) will be provided

Protocol 331-201-00079

using the Cox Proportional Hazard model with term of treatment in the model. If the null hypothesis is rejected at either interim analysis time point, the trial will be terminated for having achieved the primary endpoint of a significantly lower incidence with brexpiprazole + ADT compared with placebo + ADT. A separate Relapse Event Evaluation Committee will review and track each relapse event identified and documented. An Interim Analysis Plan will be developed to document the details of data flow and other logistical considerations relating to the interim analyses.

Table 7.4.4-1 Boundaries for Rejection of Null Hypothesis for Interim and Final Analyses		
Analysis	Number of events	2-sided alpha Level^a
Interim analysis #1 (~50%)	52	0.003051
Interim analysis #2 (~75%)	78	0.018325
Final analysis (100%)	104	0.044005

^aObtained using PASS 14 sample size software.

The interim monitoring of efficacy will be performed by an independent IARC (Section 3.7.7). Should the interim analysis be performed at a different time, different frequency, the spending function approach as originally introduced by Lan and DeMets²⁹ will be applied to adjust the critical values in order to guarantee an overall 0.05 alpha level. The spending functions corresponding to O'Brien-Fleming boundaries will be formally applied to the time-to-event analysis (using the log-rank test).

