3.7 Interim Analysis Review Committee

The Interim Analysis Review committee (IARC) is formed to independently review unblinded efficacy data for the planned interim analyses (at approximately 50% and 75% of protocol event accrual) and make recommendations to the sponsor. Details are described in the IARC Charter for the Protocol.

[figure not shown]

Figure 3-1

Trial Design Schematic

4 Sample Size and Power Justification

The primary objective of this trial is to show superiority of brexpiprazole (2 to 3 mg/day) + ADT over placebo + ADT in time to relapse of MDD signs and/or symptoms. The 2-sided log-rank test will be used to test for statistical significance of the differences between the 2 survival curves.

Based on the results from a completed randomized withdrawal trial of olanzapine/fluoxetine combination versus fluoxetine monotherapy to assess prevention of relapse in subjects with treatment-resistant depression, it is reasonable to expect that 30% of subjects who receive placebo and 16% of subjects treated with brexpiprazole will relapse in 6 months, a hazard ratio of 0.49 (brexpiprazole + ADT versus placebo + ADT) is derived. Thus, 104 relapse events are needed in this trial to reach 95% power to test the primary hypothesis of the protocol at a 2-sided 0.05 alpha level. The sample size estimates used a 1:1 randomization ratio (brexpiprazole + ADT: placebo + ADT) which allowed 2 interim looks at 50% and 75% of events accrual time points. The O'Brian-Fleming boundaries were used for sample size calculation of the interim analysis so that the first interim analysis will be conducted when 52 relapse events are available, and the second interim analysis will be conducted when 78 relapse events are available. The 2-sided alpha levels for these 2 interim analyses are 0.003 and 0.018 respectively, and the alpha left for the final analysis when 104 relapse events are available will be 0.044.

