Each subject will be followed for 26 weeks after randomization; allowing for a 20% loss to follow-up, the projected total number of subjects to be randomized into the trial is 450. Using a 1:1 randomization ratio, the number of subjects to be randomized into each treatment group is 225. Assuming approximately 68% of subjects will progress from the Stabilization Phase (Phase B) to Double-blind Randomized Withdrawal (Phase C), it is expected that 700 subjects will be enrolled into the Stabilization Phase of the trial to allow 450 subjects to be randomized. Assuming approximately 55% subjects will progress from the Acute Treatment Phase to the Stabilization Phase, it is expected that approximately 1450 subjects will be enrolled into the Acute Treatment Phase. However, only the number of relapse events (i.e., 104 events) is the determinate factor for sample size of this protocol. The other estimates, such as number of randomized subjects and number of subjects entering the Acute Treatment Phase and the Stabilization Phase, are only based on projection using assumptions that may or may not hold in this trial. Therefore, the actual number of subjects enrolled into the Acute Treatment Phase, the Stabilization Phase, or Double-blind Randomized Withdrawal Phase may vary from the projected values in order to reach the targeted 104 events.

5 Statistical Method

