5.5 Efficacy Analysis

5.5.1 Primary Efficacy Analysis

5.5.1.1 Primary Efficacy Endpoint

The primary efficacy endpoint of this trial is time-to-relapse by any criteria as defined in the blinded addendum to this protocol, measured from Week 20 (randomization) to the Double-blind, Randomized Withdrawal Treatment Phase).

Time-to-relapse (primary efficacy endpoint) is defined as meeting any of the following criteria (blinded to investigators) measured from randomization into Phase C:

- I. At the same visit, an increase on the MADRS total score of 50% from randomization and CGI-S score ≥ 4 , **OR**

- II. Hospitalization for depression, **OR**
- III. Discontinuation for lack of efficacy or worsening of depression, **OR**
- IV. Active suicidality, defined as a score of ≥ 4 on the MADRS item 10 **OR** an answer of “yes” on question 4 or 5 on the C-SSRS **OR** an answer of yes to any of the questions on the Suicidal Behavior section of the C-SSRS.

The time origin for measuring this event time is the date of randomization into the double-blind, placebo-controlled treatment phase (Phase C). Phase C Efficacy Sample is used in the primary analysis of the primary efficacy endpoint. The primary objective of statistical analysis is to compare the efficacy of brexpiprazole (2 to 3 mg/day) + ADT with that of placebo + ADT with regard to time-to-relapse. This will be achieved by testing the equality of the two survival curves by the log-rank test.

Interim analyses are planned to be performed at approximately 50% and 75% of events accrual time points using the O’Brian-Fleming boundaries for rejection of the null hypothesis. Details of the interim analyses are provided in the interim analysis plan.

A group sequential testing procedure will be employed with two planned interim analyses at approximately 50% (52 events) and 75% (78 events) events accrual time points, and a final analysis using 100% (approx. 104 events) events. The O’Brian-Fleming boundaries will be utilized in this analysis for the rejection of the null hypothesis to maintain an overall nominal significance level of 0.05 (two-sided). [REDACTED]

[REDACTED]

[REDACTED]

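### SAP 5.5.5 gives a p-value within each subgroup but plans no treatment-by-subgroup analysis, so it does not assess whether the effect differs between subgroups

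*SAP*

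**What the plan says.** SAP 5.5.5 plans subgroup analyses of the primary endpoint, time to relapse in Phase C, for four two-level factors:

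- region (US, non-US)
- gender
- race (Caucasian, non-Caucasian)
- age (below 45, 45 and above)

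Each of the eight subgroups gets an estimated hazard ratio and a nominal two-sided 95% confidence interval. In addition, a "within subgroup p-value from the log-rank test will be provided for each of the subgroups". The Cox model has treatment as its only term. The section describes its aim as exploratory and closes with a warning that positive findings may be false positives.

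The only interaction terms in the available text are by visit, in the exploratory repeated-measures model (Protocol 7.4.2.2, SAP 5.5.4.3). The COVID-19 subgroup analysis in SAP 5.5.3 follows the same within-subgroup pattern. The text of Protocol 7.4.3 (Exploratory Endpoint Analysis) is not in the public copy, so nothing can be said about it.

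The design figures are in SAP Section 4. It expects that "30% of subjects who receive placebo and 16% of subjects treated with brexpiprazole will relapse in 6 months", and from this "a hazard ratio of 0.49 (brexpiprazole + ADT versus placebo + ADT) is derived". On the number of events, the section says: "104 relapse events are needed in this trial to reach 95% power to test the primary hypothesis of the protocol at a 2-sided 0.05 alpha".

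**The concern.** A p-value computed inside one subgroup tests whether the effect in that subgroup differs from none. It does not test whether two subgroups differ from each other, which is the question a subgroup analysis is normally meant to answer. Splitting about 104 events in two lowers the power in each part, and lowers it sharply in the smaller part. One half can then be significant and the other not, although the true effect is identical in both.

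The SAP's caution points one way only. If the drug works as assumed, the likelier mistake is to read a small, non-significant subgroup as one in which it does not work. Nothing in SAP 5.5.5 warns against that. What is at stake is a misleading contrast in the trial report. The primary result, the type I error and the sample size are not affected.

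**Working it through.** **Inputs from the documents.** Hazard ratio 0.49, 104 events, two-sided alpha 0.05, 95% power and 1:1 allocation (SAP Section 4); looks at 52 and 78 events (SAP 5.5.1.1); boundary levels 0.003051, 0.018325 and 0.044005 (Protocol 7.4.4).

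**Assumptions.** The same true hazard ratio in every subgroup. Event shares from 50/50 to 90/10, because the documents give none.

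**Step 1: reproduce the plan's figure.**
- Hazard ratio = ln(1 − 0.16)/ln(1 − 0.30) = ln 0.84/ln 0.70 = 0.489, which agrees with 0.49.
- Schoenfeld events for a fixed design = 4(1.960 + 1.645)²/(ln 0.49)² = 51.98/0.509 ≈ 102.1, or 103 when rounded up. The plan states 104 with two interim looks.
- Simulating the stated boundaries at 52, 78 and 104 events gave overall alpha 0.0498 and power 95.0%. The plan's figure holds.

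**Step 2: power in each half.** With d events in a subgroup, power = Φ(|ln 0.49|·√(d/4) − 1.96), where |ln 0.49| = 0.713. For 52 events this is Φ(0.713 × 3.606 − 1.96) = Φ(0.61) = 73%.

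**Step 3: outcome for one factor.** With powers p1 and p2, the chance of exactly one p<0.05 is p1(1 − p2) + p2(1 − p1). At 80/20 this is 0.902 × 0.631 + 0.369 × 0.098 = 0.605.

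| Event split | Events | Power | Both significant | Exactly one | Neither |
|---|---|---|---|---|---|
| 50/50 | 52/52 | 73%/73% | 53% | 39% | 7% |
| 60/40 | 62/42 | 80%/63% | 51% | 42% | 7% |
| 70/30 | 73/31 | 86%/51% | 44% | 49% | 7% |
| 80/20 | 83/21 | 90%/37% | 33% | 60% | 6% |
| 90/10 | 94/10 | 93%/21% | 20% | 75% | 5% |

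The chance of exactly one passes 50% when the smaller half holds about 29% of the events (about 30 events) or fewer.

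**Step 4: variations.**
- Among simulated trials that are also significant overall at the final level, the chance of exactly one is 40% at 50/50 and 62% at 80/20.
- With 78 events, as after a stop at the second look, it is 48% at 50/50 and 63% at 80/20.
- With a weaker uniform hazard ratio of 0.60 and 104 events, it is 50% at 50/50 and 58% at 80/20.

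**Step 5: four factors together.** The four factors divide the same events, so their results are correlated and the single-factor chances cannot be multiplied. Simulation with independently crossed factor membership gave these chances of at least one factor with exactly one significant half:
- all four at 50/50: 68%, with 1.6 such factors expected
- 80/20, 70/30, 70/30 and 50/50: 85%, with 2.0 expected

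**Step 6: what an interaction analysis would do.**
- Under a uniform effect, a test at 0.05 gives a false signal in 5% of tests per factor. For at least one of four, if independent, this is 1 − 0.95⁴ = 18.5%.
- The standard error of the log ratio of hazard ratios is √(4/d1 + 4/d2). This is √(4/52 + 4/52) = 0.39 at 50/50 and √(4/83.2 + 4/20.8) = 0.49 at 80/20.
- Power to separate 0.49 from 1.0 is Φ(0.713/0.392 − 1.96) = 44% at 50/50 and Φ(0.713/0.490 − 1.96) = 31% at 80/20.
- The ratio of hazard ratios detectable with 80% power is 3.0 at 50/50 and about 3.9 at 80/20.

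**The case against.** The SAP does not rest any decision on these p-values. It calls the analysis exploratory, lists the hazard ratio and interval before the p-value, and adds a caution. The subgroups are also outside the confirmatory testing sequence in Protocol 7.4.2.1. A reader might infer that the plan judges efficacy subgroup by subgroup on significance. The documents do not support that, because no such rule is stated.

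A reader might also infer that a split verdict is the expected result for any factor under a uniform effect. That is not so at the planned size. With an even split, both halves are significant in 53% of trials and exactly one in 39%. A split verdict becomes the majority outcome for a single factor only when the events are divided about 71/29 or more unevenly, and the documents give no shares.

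Dropping the p-values while keeping the intervals does not hide the contrast either, since an interval that crosses 1 tells nearly the same story. And the interaction test is weak.

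These points limit the concern but do not remove it. An exploratory analysis should still address the question it raises, and the available plan has no comparison between subgroups. Low power is a reason to report the ratio of hazard ratios with its interval, which shows how little the data can say.

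**Conclusion.** The concern holds in limited form. SAP 5.5.5 plans within-subgroup p-values from treatment-only models and no treatment-by-subgroup analysis, so the stated method does not assess whether the effect differs. Its caution omits the error that is likelier if the drug works.

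At 104 events and a common hazard ratio of 0.49, a given factor shows exactly one significant half in 39% (50/50) to 60% (80/20) of trials. At least one of the four factors does so in about 68% to 85%. The upper figures rest on assumed uneven event shares, and the four-factor figures also assume that factor membership is independent. Even the most favourable case considered, all splits even, gives about two in three.

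This is a cheap improvement to exploratory reporting, not a threat to the trial's main conclusion.

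**What to change.** For each factor, fit one Cox model with treatment, subgroup and treatment-by-subgroup terms. Report the subgroup hazard ratios with confidence intervals, the ratio of hazard ratios with its 95% interval, and the interaction p-value, all labelled exploratory. Drop the within-subgroup p-values. Extend the caution to say that a non-significant subgroup may only reflect few events, and that a non-significant interaction does not show that the effect is the same in both subgroups.

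The cost is a few lines of SAP text and one model per factor. No new data are needed, and alpha and the primary analysis are unchanged. The drawback is the interaction test's power of about 31% to 44% for 0.49 against 1.0, which is why the ratio and its interval should carry the interpretation.
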